1 STUDY SYNOPSIS

Coordinating investigator	[name] Bravis Ziekenhuis Roosendaal [name]
Principal investigator(s)	[name] Bravis Ziekenhuis Roosendaal
Sponsor	Zimmer GmbH [name] SWITZERLAND

Rationale:

The investigational device is the femoral component of a total hip arthroplasty (THP). Total hip arthroplasty (THA) is a widely used surgical procedure with a high success rate. The survival rate of THA with revision for any reason as end point in national registries is in the order of 95% after 10 years. Mechanical reasons for revision like fatigue failure, wear or aseptic loosening have diminished. Other revision reasons like infection or component malpositioning have become the major reason for revision. Therefore further development of THP's is now focusing on other aspects than just increased survival time. Aspects like bone conservation, minimal invasive procedures, fast recovery time and short admission time are leading factors in THP development. Also the investigational device of this study is focusing on these aspects. In comparison to conventional hip prostheses it has a number of different features, like: a very high neck resection, a shallow neck resection and a short stem in combination with cemented fixation. The goal of these features is 1) to diminish the amount of resected bone and thereby to have a better starting point in case of revision and 2) to offer a hip stem which can be used more easily in combination with a minimal invasive surgical approach. Because the investigational device is only to be fixated in the metaphyseal region of the femur it is called: Metaphyseal Hip Prosthesis (MHP). Metaphyseal hip stems are not new. Several designs have been in the market for a prolonged period like the Mayo Hip from Zimmer and the Cut 2000 hip from ESKA Implants. More recently short stems like the Proxima and the Silent hip from DePuy have been introduced in particular to address the demand for minimal invasive surgery. All these stems are fixated to the bone without the use of bone cement. This makes the procedure relatively easy but also makes the stability of the implant dependent on the quality of the bone stock. In case of the MHP it is chosen to use bone cement as fixation method. This enables immediate weight bearing by the patient and makes the reconstruction less dependent of the bone quality.

In order to conserve as much bone as possible it has been chosen to use a high subcapital resection. The stem has a rather short length and the entire length remains inside the metaphyseal trabecular bone to ensure a good interdigitation at the cement-bone interface. The short length will increase the interface stresses, both shear stresses in axial loading and normal stresses due to a bending load. Therefore it is chosen to make a shallow neck resection and to add a collar to the stem which rests on the resection surface. This will increase the load transfer to the femur very proximally and will diminish the interface stresses. Proximal load transfer has the additional advantage to protect against stress shielding induced osteopaenia.

The diminished stem-cement surface and the increased stresses at the stem-cement interface are counteracted by longitudinal grooves on the anterior and posterior surface of the MHP stem. Extensive

laboratory testing has shown that the stem-cement interface is able to withstand extreme high loads on the hip joint. The whole MHP reconstruction in laboratory testing showed to have superior strength compared to the natural femur. This protocol aims at the first in vivo implantation.

Objective:**1.1.1.1 Primary objective:**

- To analyze the stability of the MHP using Roentgen stereophotogrammetric analysis (RSA) to predict the long term survival.

1.1.1.2 Secondary objective

- To analyze the short term (1 year) safety of the MHP compared to the Stanmore hip replacement.
- To analyze the short term (1 year) efficacy of the MHP compared to the Stanmore hip replacement.
- To analyze the long term (10 years) safety of the MHP compared to the Stanmore hip replacement.
- To analyze the long term (10 years) efficacy of the MHP compared to the Stanmore hip replacement using patient based questionnaires.

Study design: Single-centre prospective study with 25 patients in the study and 25 in the control group. Open, RCT (Randomized Controlled Trial) in which the MHP is compared with the standard Stanmore hip prosthesis.

Study population: Patients with osteoarthritis of the hip with no severe co morbidities.

Main study parameters/endpoints:

- Stability measured with RSA at discharge, 3, 6, 12 and 24 months postoperative.
- Safety defined as absence of serious device related complications.
- Efficacy defined as functional outcome measured with HHS and the HOOS preoperatively, 6 weeks, 3, 6 and 12 months and subsequently annually at 2-7 years and at 10 years postoperatively.
- Bone density measured using DEXA preoperative and 6 weeks, 1, 2 years postoperative.
- Quality of life measured with the SF12 preoperatively, 6 weeks, 3, 6 and 12 months and subsequently annually at 2-7 years and at 10 years postoperatively.

Nature and extent of the burden and risks associated with participation, group relatedness:

The MHP has not been implanted in human before. Therefore risks of the MHP in vivo are unknown. Nevertheless, preclinical tests of the MHP showed promising results.

All potential risks for a hip prosthesis are reported in section A4.4.

For the study additional traditional and RSA X-rays need to be made, as well as additional DEXA scans. Therefore the radiology exposure will increase with 6 mSv for the total study (10 years). The average annual natural dose is 2 mSv.

The questionnaires will take approximately 10 minutes at each control visit. The RSA and DEXA scans will take approximately 15 minutes each.

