2 STATISTICAL ANALYSIS PLAN

Statistical design, method and the analytical procedures

The patient characteristics of both groups will be compared using the chi square test for categorical data, the t-test for normal divided continuous data and non parametric test for not normally divided continuous data.

If the patient characteristics are not significantly different, no correction will be made, otherwise the data will be corrected using multiple variation analysis.

Continuous outcome variables will be analyzed with general linear modelling which a Bonferoni post hoc test and the data will be compared to the preoperative data.

Clinical data (HHS, HOOS and SF-12) will be presented using 95% confidence intervals while comparing the results between the MHP and Stanmore prostheses.

Differences in the various clinical and laboratory outcomes between treatment groups will be presented with their 95% confidence intervals.

b) Sample size

50 patients. 25 in each group.

This item is described in session A.5.2

c) Level of significance and the power of the clinical investigation

Not relevant, since the power is based on literature (session A 5.2).

d) Expected drop-out rates

Not relevant, since the power is based on literature (session A 5.2).

e) Pass/fail criteria to be applied to the results of the clinical investigation

Table 2: Criteria for decision to continue the study.

	Pass
Safety:	Less than 10% device related complications.
Efficacy	Functional improvement and pain reduction measured with the Harris Hip Score and HOOS compared to preoperative score within the same range as the improvements for the Stanmore hip.
Correctly implanted	Based on standard radiographs 
- A leg length increase between -10 and 5 mm.- Laterization of the head between + 5 and -10 mm.- Circumferential cement mantle.- The bone plug is placed 1 to 3 cm below the prosthesis.

	
- Absence of cement leakage below plug.- Absence of radiolucency between prosthesis and cement in all Gruen zones.
--	---

f) Provision for an interim analysis, where applicable

After 20 patients are included (10 MHP and 10 Stanmore), a 6 weeks waiting period will be used after which the surgeon will decide if the prosthesis is safe according to criteria defined above. An independent orthopaedic surgeon will evaluate the X rays of the first 10 patients with the MHP prosthesis.

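### The one endpoint defined for the 1-year and 10-year safety comparisons counts only serious device-related complications; relatedness is undefined and any-cause revision is not listed as an outcome.

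*Combined protocol and SAP*

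**What the plan says.** Section 1.1.1.2 (Secondary objective) sets two comparative safety objectives: "To analyze the short term (1 year) safety of the MHP compared to the Stanmore hip replacement" and "To analyze the long term (10 years) safety of the MHP compared to the Stanmore hip replacement". The list of main study parameters that follows gives a single definition for both: "Safety defined as absence of serious device related complications". An event must therefore pass two filters, seriousness and relatedness to the device. The available text defines neither and names no assessor.

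The Rationale in the synopsis says that mechanical causes of revision have declined and adds: "Other revision reasons like infection or component malpositioning have become the major reason for revision". It also gives a background figure: "The survival rate of THA with revision for any reason as end point in national registries is in the order of 95% after 10 years".

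The SAP (section 2) uses other event sets elsewhere. The safety row of Table 2, under item (e), reads "Less than 10% device related complications", with no seriousness filter, and a separate row covers correct implantation on radiographs. Item (g) would terminate the study on a significant excess of complications and adverse events in the MHP group, with neither filter. Item (i) has adverse events reviewed in the first 20 patients. Revision appears in the SAP only in item (k), as a trigger for carrying the last measured data forward.

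**The concern.** In a randomised comparison, background events fall on both arms by chance, so the arms can be compared without deciding case by case what the device caused. Adding that decision has two costs.

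First, the trial is open. Whoever attributes an event can know which stem the patient has, and the same infection or malposition could be called device related in one arm and procedural in the other. The direction of any bias cannot be predicted. The synopsis also says that the in vivo risks of this first-in-human stem are unknown, which leaves little basis for attribution.

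Second, infection and malposition are events that can readily be put down to the procedure. If they are, a patient revised for either counts as safe at 1 or 10 years. Under item (k) the same patient's last measured functional data are carried forward, so the revision might show in neither the safety nor the efficacy result.

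**Working it through.** The plan states no figure for this endpoint, so there is none to reproduce. The check sets the event definitions side by side and then shows how few events are at stake.

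**1. The three event sets**

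| Place | Must be serious? | Must be device related? | Use |
|---|---|---|---|
| Synopsis, main study parameters | Yes | Yes | Endpoint of the 1-year and 10-year safety objectives |
| SAP item (e), Table 2, safety row | No | Yes | Decision to continue |
| SAP item (g) | No | No | Termination |

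Take a patient revised for infection. Item (g) counts the event. The synopsis endpoint and Table 2 count it only if someone judges it device related. Only the synopsis row defines the endpoint of the two comparative objectives.

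**2. Events available**

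Inputs: n = 25 per arm (SAP item (b): "50 patients. 25 in each group"); any-cause revision by 10 years p = 1 − 0.95 = 0.05 (Rationale). Assumptions: the background rate applies to each arm, patients are independent, and 10-year follow-up is complete. Losses or deaths would lower the counts.

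- Expected revisions per arm: 25 × 0.05 = 1.25, or 2.5 in both arms.
- Chance that an arm has none: 0.95^25 = 0.277, about 28%.

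**3. What a filter could remove**

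The documents do not say what share s of revisions would be judged unrelated to the device, so s is an assumption shown as a range. Expected count = 25 × 0.05 × (1 − s); chance of none = [1 − 0.05 × (1 − s)]^25.

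| Assumed s | Expected per arm | Chance of none |
|---|---|---|
| 0 | 1.25 | 28% |
| 25% | 0.94 | 38% |
| 50% | 0.63 | 53% |
| 75% | 0.31 | 73% |

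Only the first row rests on the documents' own figures.

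**4. What the wider endpoint can show**

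With Fisher's exact test at an assumed two-sided 0.05 and 25 per arm, power is about 20% for 5% against 20%, and about 55% for 5% against 30%. Observed counts of 0/25 against 5/25 give p = 0.0502. If an arm shows no events, the exact two-sided 95% upper limit is 1 − 0.025^(1/25) = 13.7%. Widening the endpoint gives a complete count that does not depend on attribution, but not a powered test.

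**The case against.** The strongest reply is that the plan does look at these events. Item (g) compares all complications and adverse events between groups, which would include infection. Item (i) reviews adverse events early, and Table 2 has its own radiographic criterion for position. This defeats one tempting inference, that the plan's whole safety assessment rests on serious device-related events. It does not repair the endpoint. These are continuation or termination rules, and the independent X-ray review covers only the first 10 MHP patients, with no Stanmore comparison.

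Second, nothing in the text says that infection or malposition is unrelated to the device. Sections A4.4 (risks) and A.5.2 are cited but not part of the available text, and a definition may sit in one of them or elsewhere. A reader might infer that such revisions are excluded; the documents support only that they may be.

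Third, a reader might treat the 95% survival figure as the trial's benchmark. It is background for the whole hip replacement, no objective or criterion refers to it, and the investigational device is the femoral component alone. A count of stem revisions would not match it.

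Fourth, the proposed outcomes also involve unblinded judgement, because the decision to revise and the grading of seriousness are made in an open trial. That stands. Dropping attribution removes one source of bias, not all.

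Fifth, the gain in statistical information is small at 25 per arm. That also stands.

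**Conclusion.** The concern holds for the endpoint of the two comparative safety objectives. As written, an undefined judgement by an unnamed assessor in an open trial decides which events count, and revision for any reason is not an outcome. At the background rate about 1.25 revisions per arm are expected by 10 years, with a 28% chance of none, so even one reclassified event can change the reported result.

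The conclusion does not depend on any share of revisions being screened out; the 38% to 73% figures are illustrations under assumed shares. It would change if an unavailable section defined relatedness to cover infection and malposition, named a blinded assessor, or listed any-cause revision as an outcome. The primary RSA objective is unaffected. The change is worth making for completeness and to reduce attribution bias. It will not make the safety comparison confirmatory.

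**What to change.** For the 1-year and 10-year safety objectives, report by randomised arm, with 95% confidence intervals:

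1. revision of any hip component for any reason, with stem revision shown separately and the result also given as revision-free survival;
2. all serious complications of the operated hip, regardless of attribution.

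Keep device-related complications as a supportive breakdown by cause, with relatedness and its assessor defined. Reconcile the event sets in the synopsis, Table 2 and item (g), or state why each differs. State that with 25 per arm the comparison is descriptive, and how deaths and losses to follow-up are handled in the survival estimate.

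The cost is mainly wording in the endpoint list and SAP. Some unrelated events will enter both arms, and complication rates will look slightly less favourable. One point needs confirming: the available text does not describe recording of revisions and complications through 10 years. The questionnaire schedule runs annually to year 7 and then to year 10, so revisions in that last interval, with their dates and causes, would have to be obtained at the 10-year contact or in another way.

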2 STATISTICAL ANALYSIS PLAN

Statistical design, method and the analytical procedures

The patient characteristics of both groups will be compared using the chi square test for categorical data, the t-test for normal divided continuous data and non parametric test for not normally divided continuous data.

If the patient characteristics are not significantly different, no correction will be made, otherwise the data will be corrected using multiple variation analysis.

Continuous outcome variables will be analyzed with general linear modelling which a Bonferoni post hoc test and the data will be compared to the preoperative data.

Clinical data (HHS, HOOS and SF-12) will be presented using 95% confidence intervals while comparing the results between the MHP and Stanmore prostheses.

Differences in the various clinical and laboratory outcomes between treatment groups will be presented with their 95% confidence intervals.

b) Sample size

50 patients. 25 in each group.

This item is described in session A.5.2

c) Level of significance and the power of the clinical investigation

Not relevant, since the power is based on literature (session A 5.2).

d) Expected drop-out rates

Not relevant, since the power is based on literature (session A 5.2).

e) Pass/fail criteria to be applied to the results of the clinical investigation

Table 2: Criteria for decision to continue the study.

	Pass
Safety:	Less than 10% device related complications.
Efficacy	Functional improvement and pain reduction measured with the Harris Hip Score and HOOS compared to preoperative score within the same range as the improvements for the Stanmore hip.
Correctly implanted	Based on standard radiographs 
- A leg length increase between -10 and 5 mm.- Laterization of the head between + 5 and -10 mm.- Circumferential cement mantle.- The bone plug is placed 1 to 3 cm below the prosthesis.

	
- Absence of cement leakage below plug.- Absence of radiolucency between prosthesis and cement in all Gruen zones.
--	---

f) Provision for an interim analysis, where applicable

After 20 patients are included (10 MHP and 10 Stanmore), a 6 weeks waiting period will be used after which the surgeon will decide if the prosthesis is safe according to criteria defined above. An independent orthopaedic surgeon will evaluate the X rays of the first 10 patients with the MHP prosthesis.

g) Criteria for the termination of the clinical investigation on statistical grounds

- A significant decrease in functional improvement in the MHP group compared to the Stanmore group.
- A significant increase in complications and adverse events in the MHP group compared to the Stanmore group.

h) Procedures for reporting any deviation(s) from the original statistical plan

The used statistical technique depends on the deviation of the variables. Therefore, the exact statistical technique will be determined during the evaluation and will be described in the report.

i) Specification of subgroups for analysis

The first 20 patients will be analyzed for adverse events and function to decide whether the study will continue.

j) Procedures for accounting for all data

The data will be monitored for completeness. If data is complete the file will be closed. If corrections to data are made after closure, the reason for change will be noted. If data is missing the cause will be noted on a specific document. After analysis the number of patients in each subgroup at each time interval will be noted in the tables.

k) Treatment of missing, unused or spurious data, including drop-outs and withdrawals

The study will be performed according to the intention to treat principle. If the patient is revised the last measured data will be carried forward. The data will be analyzed using general linear modelling which can account for some missing data.

l) A justification for excluding particular information from the testing of the hypothesis

Not relevant.

m) In case of multi-centre clinical investigations, the minimum and maximum number of subjects to be included for each centre

Not relevant.

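### A baseline significance test decides whether outcomes are adjusted, and the preoperative value is not named as a covariate for HHS, HOOS, SF-12 or DEXA

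*Combined protocol and SAP*

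**What the plan says.** The opening paragraphs of SAP section 2 first test the randomised arms against each other at baseline: "The patient characteristics of both groups will be compared using the chi square test for categorical data", with a t-test or a non-parametric test for continuous variables. The result then selects the analysis: "If the patient characteristics are not significantly different, no correction will be made, otherwise the data will be corrected using multiple variation analysis". The characteristics are not listed, and the correction method is not described further.

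For the outcomes, "Continuous outcome variables will be analyzed with general linear modelling", with a Bonferroni post hoc test, and "the data will be compared to the preoperative data". Treatment differences are to be shown with 95% confidence intervals. No covariate is named.

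The synopsis (Main study parameters/endpoints) shows that preoperative values exist: "Efficacy defined as functional outcome measured with HHS and the HOOS preoperatively" and at later visits. SF-12 and DEXA are also measured before surgery. RSA starts at discharge and has no preoperative value.

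Function also feeds decisions about the trial. Item g) lists as a ground for termination "A significant decrease in functional improvement in the MHP group compared to the Stanmore group". Item i) says "The first 20 patients will be analyzed for adverse events and function to decide whether the study will continue". Table 2 judges efficacy by improvement on the preoperative score. On method, item h) says that "the exact statistical technique will be determined during the evaluation and will be described in the report".

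**The concern.** Under randomisation any baseline difference is due to chance, so the baseline test has nothing to find. Whether a gap matters depends on its size and on how strongly the variable predicts the outcome, and the p-value does not measure the second. A gap just short of significance in a strong predictor stays uncorrected, while a significant gap in an irrelevant variable triggers correction. Because the characteristics are undefined, it is unclear whether preoperative scores are among those tested. The rule speaks of the data in general, so on its face it also reaches the primary RSA outcome.

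Separately, the preoperative value is usually the obvious covariate for a later measurement of the same scale, and the plan does not commit to it. The references to improvement and to comparison with preoperative data suggest change scores. That is a reading, not a stated method.

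At stake are the width of the confidence intervals for HHS, HOOS, SF-12 and DEXA, and estimates that shift when the arms happen to start unequal. The functional comparison in item g) is affected too. For every outcome, a chance result decides which analysis is reported.

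**Working it through.** **Inputs.** From the documents: 25 patients per arm (item b). They give no correlation, SD, significance level or list of characteristics, and the sample size reasoning is referred to section A.5.2, which is not in the supplied text. No plan figure is therefore in dispute or reproducible, and what follows is illustration. Assumed: one follow-up visit, no missing data, bivariate normal scores, two-sided 5% tests, follow-up SD 1, preoperative SD k = 0.7, 1 or 1.4, and preoperative-to-follow-up correlation ρ = 0.3, 0.5 or 0.7. Triplets below are in that order of ρ.

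**Step 1: gap needed for significance.** t(0.975, 2n−2) × √(2/n). With n = 25: 2.011 × 0.2828 = 0.569 preoperative SD. With n = 10: 2.101 × 0.4472 = 0.940 SD. Smaller gaps go uncorrected.

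**Step 2: chance of triggering correction.** For m independent characteristics each tested at 5%, 1 − 0.95^m gives 14% (m = 3), 23% (m = 5) and 40% (m = 10). This applies to any outcome under the rule, RSA included.

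**Step 3: change score against ANCOVA, no baseline test on the score.** Variance excess = (k² + 1 − 2kρ) / [(1 − ρ²)(1 + 1/46)] − 1, where 46 = 2n − 4. For k = 1, ρ = 0.5: 1 / (0.75 × 1.0217) − 1 = 30%. This is the case where preoperative scores are not among the tested characteristics.

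**Step 4: the rule applied to the preoperative score.** Simulation, 100,000 trials per setting: ANCOVA if the preoperative t-test is significant, change score otherwise, compared with ANCOVA always.

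| k | Variance excess, no test (formula) | Variance excess, rule applied | Mean 95% CI width excess, rule applied |
|---|---|---|---|
| 0.7 | 15%, 3%, −2% | 11%, 2%, −2% | 7%, 2%, −1% |
| 1 | 51%, 30%, 15% | 37%, 22%, 11% | 22%, 14%, 7% |
| 1.4 | 128%, 104%, 92% | 94%, 75%, 67% | 49%, 41%, 37% |

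If the default is the follow-up score alone, the variance excess under the rule at k = 1 is 5%, 22%, 67%. At ρ = 0.9 and k = 1, possible for DEXA, the change-score excess is only 2% to 3%.

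**Step 5: power, rule with change scores v ANCOVA.** True difference 0.8 SD:
- k = 0.7: 77% v 82%, 88% v 89%, 97% v 97%
- k = 1: 66% v 82%, 80% v 89%, 95% v 97%
- k = 1.4: 49% v 82%, 62% v 89%, 81% v 97%

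True difference 0.5 SD, k = 1: 31% v 43%, 41% v 51%, 61% v 67%.

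**Step 6: shift from an unflagged gap.** A change score over-corrects by (1 − ρ/k) times the raw gap; the sign reverses if ρ > k. In about 11% of trials the gap exceeds 0.4 SD but is not significant. In those trials the estimate shifts by 0.33, 0.24, 0.14 follow-up SD at k = 1; by 0.19, 0.09, 0.00 at k = 0.7; and by 0.52, 0.42, 0.33 at k = 1.4. The shift goes for or against MHP equally often.

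**Step 7: type I error.** With change scores as default, 3.5% to 5.0% across these settings. With follow-up scores as default (k = 1, 40,000 trials per setting), 3.8% to 4.8%.

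**Step 8: first 20 patients.** The figures above do not describe that decision. If it used the same test at 10 per arm, power for 0.8 SD at k = 1 would be 29% v 41%, 39% v 47%, 59% v 63%.

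**The case against.** The strongest reply is that only the baseline-test rule is written in the plan. The missing covariate is non-specification in a short SAP: a general linear model can hold the preoperative value, Table 2 and the methods paragraph do use it as a comparator, and item h) leaves the technique open. Preferring ANCOVA to change scores is then largely a matter of efficiency, and the size of the gain rests on assumptions that run from a small loss to a large gain. This stands as a limit on the size. It does not rescue the plan, because the rule's default is no correction, and leaving the choice until evaluation in an open-label trial is itself a reason to settle it now.

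Several narrower points also stand. Type I error control is shown only for one test on one score at one visit, not for several characteristics, an undefined correction or repeated visits. A repeated-measures model could give a different precision loss. The reach to RSA follows from the general wording, since the sentence does not name RSA. Item g) does not say which test is used or when, and the decision after 20 patients is partly the surgeon's judgement against Table 2. Finally, these four outcomes are not the primary objective, and no average bias is claimed.

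**Conclusion.** The concern holds. The plan explicitly lets a chance p-value choose the reported analysis, and it names no preoperative covariate for four outcomes that have one. Confidence is high on those two facts and lower on the size of the loss.

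At 25 per arm with equal SDs and correlations of 0.3 to 0.7, following the rule with change scores costs roughly 11% to 37% in variance and 2 to 16 points of power for a 0.8 SD difference (97 − 95 and 82 − 66). The loss can be nil where the preoperative SD is smaller than the follow-up SD, and it is larger where the preoperative SD exceeds it. It is likely small for DEXA if the correlation is near 0.9 and change scores are used. There is no sign of type I error inflation in the cases simulated. For RSA the precision figures do not apply; the problem there is only that a chance baseline result may switch the analysis. This should be corrected, but it does not by itself invalidate the trial.

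**What to change.** Delete the rule that ties correction to baseline significance, for all outcomes, and report baseline characteristics descriptively by arm. Add to section 2 that every between-arm comparison of HHS, HOOS, SF-12 and DEXA, including the functional comparison in item g), includes the preoperative value of the same measure as a covariate, whatever the baseline table shows. For RSA, list any covariates in advance or state that there are none.

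The cost is a short SAP edit and one degree of freedom per model, with no new data. Where change scores are already near optimal (k = 0.7, ρ = 0.7), the covariate costs about 2% in variance at 25 per arm (1/46). At 10 per arm the same factor is 1/16, about 6%, and power there for a 0.8 SD difference is 63% against 65%.

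### In the supplied text, Table 2's limit on device related complications has one dated use, at 10 MHP stems, and none while the other 15 stems are implanted

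*Combined protocol and SAP*

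**What the plan says.** The synopsis (burden and risks) states "The MHP has not been implanted in human before" and "Therefore risks of the MHP in vivo are unknown". The sample size in SAP item (b) is "50 patients. 25 in each group".

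Item (e) is headed "Pass/fail criteria to be applied to the results of the clinical investigation", and its table is captioned "Table 2: Criteria for decision to continue the study". The safety row reads "Less than 10% device related complications".

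Item (f) dates the use of those criteria: "After 20 patients are included (10 MHP and 10 Stanmore), a 6 weeks waiting period will be used". The surgeon then judges safety against them, and an independent orthopaedic surgeon reads the radiographs of the first 10 MHP patients. Item (i) confirms the scope: "The first 20 patients will be analyzed for adverse events and function to decide whether the study will continue".

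Item (g) allows termination if complications and adverse events are significantly more frequent with the MHP than with the Stanmore. It gives no date, test or significance level. The synopsis also plans 1-year and 10-year safety comparisons, RSA to 24 months and clinical follow-up to 10 years, but attaches no complication limit or action to any of these.

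**The concern.** Table 2 is the only numerical safety limit in the supplied text, and its one dated use comes when 10 of the 25 MHP stems are in place, with about 6 weeks of follow-up on the latest of them. Fifteen stems follow. No later date is given for comparing the count with the limit, either for those 15 or for complications that appear in the first 10 after the look.

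The one remaining termination criterion on complications, item (g), asks a different question: whether the MHP is significantly worse than the Stanmore, not whether it has exceeded the sponsor's own limit. In arms of this size, the second can happen long before the first. A stem that passes the early look could therefore exceed the limit while implantation continues, with no dated step at which this would be noticed.

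**Working it through.** **Inputs.** From the documents: 25 MHP stems, 10 at the look, limit under 10%. Assumed: true complication rate *p* (not in the documents, so shown as a range), at most one complication per stem, the limit read as a proportion of MHP stems, and Fisher's exact test at two-sided 0.05 for item (g). The plan's sample size cannot be reproduced, because its basis is in section A.5.2, which is not supplied. It is not needed here.

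**1. Stems after the look.** 25 − 10 = 15, and 15/25 = 60%.

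**2. What a pass shows.** 1/10 is 10%, which is not under 10%, so only 0/10 passes. P(pass) = (1 − p)^10 = 0.349, 0.197 and 0.107 at p = 0.10, 0.15 and 0.20. The one-sided 95% upper bound after 0/10 is 1 − 0.05^(1/10) = 25.9%. The next 15 stems carry 15p = 1.5, 2.25 and 3 expected complications.

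**3. Can item (g) stand in for the limit?** At 25 per arm, with no Stanmore events, the two-sided p-value for x MHP events is 2·C(25,x)/C(50,x):
- x = 3: 2 × 2300/19600 = 0.235
- x = 5: 2 × 53130/2118760 = 0.050 (0.0501, not significant)
- x = 6: 2 × 177100/15890700 = 0.022

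So 6 versus 0 is needed (7 versus 1 if one Stanmore event occurs, p = 0.049). Table 2 is breached at 3/25 = 12%. Exact power of (g) at 20% versus 5% is 19.8%. After a 0/10 pass, the chance of 3 or more among the other 15 stems is 3.6%, 18.4% and 60.2% at p = 0.05, 0.10 and 0.20.

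**4. Re-applying the limit at 15 and 20 stems.** 1/15 = 6.7% and 1/20 = 5% pass; 2/15 = 13.3% and 2/20 = 10% do not. With every complication visible when counted, P(flag by stem 20 | 0/10) = P(X ≥ 2), X ~ Bin(10, p) = 1 − (1 − p)^10 − 10p(1 − p)^9.

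| True rate | P(0/10) | Flag after a pass | Unconditional (product) |
|---|---|---|---|
| 5% | 0.599 | 0.086 | 5.2% |
| 10% | 0.349 | 0.264 | 9.2% |
| 15% | 0.197 | 0.456 | 9.0% |
| 20% | 0.107 | 0.624 | 6.7% |

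At 8%: 1 − 0.434 − 0.378 = 0.19. At 9%: 1 − 0.389 − 0.385 = 0.23.

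**5. Late complications, 20% eventual rate, half visible at the first look.** P(pass) = 0.9^10 = 0.349. Flag rates after that pass:
- Nothing new in the first 10 stems, half visible in stems 11–20: P(X ≥ 2), X ~ Bin(10, 0.10) = 0.264.
- By the count, 75% visible in the first 10 and 25% in stems 11–20: per-stem probabilities are (0.15 − 0.10)/0.90 = 0.056 and 0.05. P(0) = 0.944^10 × 0.95^10 = 0.338 and P(1) = 0.377, so the flag rate is 0.285, about 29%.
- All visible in the first 10, half in stems 11–20: per-stem probabilities are 0.111 and 0.10, so the flag rate is 0.64.
- Accrual so fast that nothing new is visible: near 0.

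No enrolment rate is given, so the documents do not settle which case applies.

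**The case against.** A reader might infer that 15 stems, and everything that happens later to the first 10, fall outside any scheduled check. The documents do not support that. Follow-up visits and RSA are scheduled for every patient, a 1-year safety comparison is planned, and item (g) is not limited to the first 20 patients. The heading of (e) could also be read as covering the final results, although those come after implantation has ended. What stands is narrower: no dated re-application of the limit.

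Nor can it be said that the plan as a whole lacks later monitoring. The text refers to sections A4.4 and A.5.2, which are not supplied, and (g) concerns statistical grounds only, so other rules may exist elsewhere.

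The gain is also modest. If complications show promptly, the existing look already stops a 10%, 15% or 20% stem in 65%, 80% and 89% of trials, which is why the unconditional yield is only 9%, 9% and 7%. Most flags come at stem 20, with 5 stems left: a flag by stem 15 has probability 8%, 16% and 26% after a pass. If implantation stopped at the flag, 0.17, 0.47 and 0.89 expected complications would be avoided after a pass (0.06, 0.09 and 0.10 unconditionally). This is fair. However, it assumes that the first look sees everything. If only half shows by then, a 20% stem passes 35% of the time rather than 11%, and the unconditional yield in the first two late cases is 0.349 × 0.264 = 9.2% and 0.349 × 0.285 = 9.9%.

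Finally, the number and timing of looks are a design choice, and no passage contradicts another. That is correct: this is a gap, not an error.

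**Conclusion.** The point holds as a gap in the supplied text. Table 2's limit has one dated application, and for 15 of 25 first-in-human stems the only later termination criterion on complications is undated and, at 25 per arm, needs about 6 versus 0 where 3 of 25 already exceeds the limit.

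Re-applying the limit is worth its small cost, but its benefit should not be overstated. The 26%, 46% and 62% flag rates are conditional on a 0/10 pass and on complications being visible when counted. With late complications, the 20% figure falls to about 26–29%, or towards zero with fast accrual; it holds at about 64% only if all late events in the first 10 have appeared by the count. All complication rates, the visibility fractions, and the test and level used for (g) are assumptions. The conclusion would change if an unsupplied section already dates a later review against the limit.

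**What to change.** In item (f), state that the Table 2 safety row, unchanged, is re-applied when 15 and 20 MHP stems have been implanted. The count should cover all device related complications known in MHP patients at that date, including those in the first 10 since the look, and go to the independent surgeon already named in (f). If another section already provides this, a cross-reference in (f) is enough. The limit and the consequence of reaching it remain the sponsor's to define.

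The cost is one sentence and two short tables from data already collected at a single centre, with no new waiting period unless the limit is reached. The downside is an unneeded pause. For stems whose true rate meets the limit, and that passed the first look, this happens in about 9% of cases at a true rate of 5%, 19% at 8% and 23% at 9%.
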